### **3.4.2 Breath Alcohol Content**

After the study introduction, the RA will ask the individual for verbal permission to continue with the BAC and eligibility screening. If the individual does not wish to continue, they will be rescheduled for a screen within the next 2 weeks, or referred back to SWNARC for further treatment. Reasons for non-participation will be documented in the MICRA Screening Log. If the individual agrees to the BAC and SCID, the RA will collect the individual's breath alcohol content level and record the information on the MICRA Screening & Consent Form. All individuals should be informed that their BAC must be .05 or less for research interviews, or they will be rescheduled for another day.

If the person's BAC level is  $> 0.05$ , the RA will inform the individual of his or her BAC level and that it is not safe to drive. The RA will inquire about the individual's transportation to and from the screening. The RA may call someone to pick the person up, or let him or her stay in the office until the BAC is less than or equal to .02. If the person insists on driving away, the RA will inform him or her that they have to call the police but will not try to keep him or her from leaving the building. If  $BAC > .05$ , the individual must reschedule the screening for another day. Even if an individual has a BAC of .05 or lower, the RA has the right to not continue with the consent and screening if the individual smells like alcohol or seems intoxicated or impaired by other drugs. It is important to be safe. In such cases, the RA will ask the person to reschedule for another day.

If the BAC reading is less than or equal to .05, continue with the screening. The BAC must be less than or equal to .05 mg/dl in order for the person to sign the consent form. At this point, potentially eligible participants will be given a Screening Identification Code and evaluated for study admission. The Screening Identification Code will also serve as the study ID number if the individual becomes a part of the study. Screening Identification Codes will only be used once, thus there may be gaps between Study ID numbers reflecting screened individuals who did not meet eligibility criteria for the study. Study ID numbers will start with 1 for Phase 1 (e.g., 1001, 1002) and start with the number 2 for Phase 2 (e.g., 2001, 2002).

### **3.4.3 Screen for basic eligibility criteria**

Prior to beginning the formal screening process, the RA will determine if the individual meets the following eligibility criteria (use Eligibility Checklist), and does not meet any exclusion criteria:

- 18 years or older
- Seeking treatment for substance use disorder
- Willing to be randomized
- Southwest Native American tribal member
- Lives in Southwest Native American tribe, Ramah, or Vanderwagon
- Willing and able to participate in English

- Can provide a phone number or address for at least 1 locator at the baseline interview (RA will follow-up with participant for more locator information)
- Will not be gone more than 14 days during the 16 week treatment period
- Is not actively psychotic; does not have a chronic mental illness
- No major cognitive impairments

The intake technician will evaluate some of these criteria, but the RA will double-check the criteria to avoid protocol violations. Some of these can be done indirectly: for example, inquiring about where the participant lives in casual conversation. If the participant becomes ineligible at any time during the screening process, staff should use their discretion when informing the person of the reason(s) for their ineligibility. The eligibility criteria should be kept somewhat private so individuals do not misrepresent the criteria they meet, or hear about the criteria from other individuals and assume they do not meet them. If the participant is not eligible for the study because of any of the reasons above, the Research Assistant will inform the Intake Technician and re-connect them with the SWNARC referral process. Reasons for ineligibility will be documented in the MICRA Screening Log.

#### **3.4.5 Screening Failures**

A screening failure is defined as someone who completed the screen but does not meet eligibility criteria. This information will be captured in the MICRA Screening Logs. Research staff can inform the participant as to why they are ineligible but should use

good judgment when doing so (e.g., if the person did not drink enough to qualify for study participation and they are informed of this, they might drink more to be included).

*(If **EXCLUDE**)* Those are all the questions that I have for you. I would like to thank you for your time and cooperation. Unfortunately, you do not meet the criteria for inclusion in our study. We will refer you back to Southwest Native American Recovery Center so that you can continue the intake process there, if you would like. *(Document the referral in the MICRA Screening Log, or indicate if the referral is declined.)*

*(If **CAUTION**)* Those are all the questions that I have for you. I would like to thank you for your time and cooperation. It looks as though you may meet the basic criteria for inclusion into our study, but I will need to discuss this with my supervisor before I will know. Also, we may need to ask you some more detailed questions to help us decide if we can include you. *(Ask for a phone number where they can be reached. Inform them that all information is confidential, and that we will not disclose in our call that we are a research study – we will leave our first name and phone number only. If they refuse to give a phone number, then ask them if there is a time when they could call back after you have had a chance to discuss things with your supervisor).*  
*(Document, in the MICRA Screening Log, the name and phone number (if provided), whether the person said they would call back, or whether the person declined to follow through)*

#### **3.4.6 The Research Timeline Handout**

Provide a copy of the handout **“Your Roles and Responsibilities as a Research Volunteer”** (Appendices D and E) to individuals who meet study eligibility criteria and review the content of the form. Potential participants should be informed of the study specifics in a manner that increases willingness to participate. For example, benefits of participation should be highlighted, incentives for study participation and retention should be clear and participants should also be alerted to inadvertent non-compliance with assessment procedures. Be sure to cover the following points:

- Difference between treatment and research
- Structure of the interviews (listed on the timeline), including a Breathalyzer and oral fluid drug test at each visit, as well as paper and pen self-report forms, and interviews.
- Compensation schedules; explain that the participant will be compensated after completing each follow-up visit.
- The importance of continuing in research follow-up interviews even if the participant decides to discontinue treatment
- The importance of complete and accurate data
- We will be giving reminder letters and calls

Explain that the RA will collect data during the treatment phase of the study, and will also collect data during the follow-up phase. During the latter phase the participant will only be meeting with the RA. This data will be used to determine how helpful this particular treatment is.

Ask the participant if he/she has any concerns regarding the assessments, the time commitment, or any other aspect of the study. Respond to any questions that the participant brings up, focusing primarily on clarifying study procedures and reinforcing the importance of the research participant's role. If the participant identifies any concerns such as childcare, transportation, etc., refer these issues first to the Program Coordinator ([name]) for resolution, and then to the Principal Investigator ([name]) if further clarification is needed.

### **3.4.7 Informed Consent**

It is important for the staff person to acknowledge the full range of potential risks, costs, and discomforts associated with the experimental design, as well as anticipated benefits of participation. Being "fully informed" means that the participant has had an opportunity to discuss concerns about any of the assessment, treatment, or follow-up procedures, and has had an opportunity to consider alternatives to participation in the study. This includes explaining that participants randomized to SWNARC for Phase II will need to go through the SWNARC assessment, and that information collected for the research assessment will not be shared with SWNARC. The participant should be given time to decide whether to participate, which may include taking the consent home and discussing the study with family members. If the individual decides to take the consent home to consider the study, the RA will ask him or her to stop by or call the next day to inform the RA about his or her decision regarding study participation. The RA will sign the translation line on the consent form if any part of the consent was translated into Southwest Native American language. Once participants sign the consent and HIPAA forms, they will be given a carbon copy for their own records, as well as the RA's card with contact information. All consent forms will be kept in the MICRA offices. If the RA is unsure whether the individual meets full eligibility criteria, she may tell the individual that his or her enrollment in the study is pending review by the Principal Investigator (see 3.4.5). The date of the consent will be recorded in the Participant Enrollment Log.

### **3.5 Transitioning to the Baseline Assessment**

If an individual is eligible for and interested in the study and signs the consent form, the next step is to continue with the baseline interview. In some cases, the RA will have time to continue with the baseline interview immediately following the screening and consent. This will depend on the RA and participant's availability and energy levels. If the participant does not continue with the baseline interview, then the RA will schedule another time to complete the baseline interview. The scheduled baseline interview date will be recorded in the Participant Enrollment Log. The baseline interview must be completed within two weeks of the screening, and the RA should call to remind the participant about the baseline interview the day before it is scheduled. The RA will say something along these lines: "Okay [insert name], now we need to schedule your first research appointment. It would be best if we could schedule it for tomorrow, but if that doesn't work for you we need to schedule it within the next week. The next visit will last approximately three to four hours. You will meet with me to fill out some paper questionnaires and complete a short interview." If the participant misses three scheduled baseline interview appointments, they will be referred back to SWNARC for treatment there. Only individuals who complete the baseline interview (and are randomized if in

Phase II) will count towards the total number of study participants. Participants who are randomized but do not begin treatment will still be invited to continue on with the research assessments.

## **Chapter 4: Baseline Assessment**

### **4.1 Overview of Baseline Assessment**

The baseline assessments can be divided into two days if the RA deems that it would benefit the participant. However, to prevent data loss the baseline assessment should be completed on the same day, if possible, and must be completed within two weeks of the initial screening. If the baseline interview happens on multiple days, all of these days must be in the same week and the same baseline checklist can be used for all meetings.

Participants will be given water and snacks if they would like. They will also be given ample opportunities to take breaks during the baseline assessment. The baseline assessment consists of a BAC, oral fluid drug test, and self-report and interviewer-administered questionnaires (see Table 4.1).

At the baseline interview, the RA will remind the participant of her role: *to collect research data before, during and after treatment in order to see how well the treatment is working*. She will explain that research staff are separate from the treatment staff, and that information obtained from the participant during follow-up assessments will not be shared with the counselors. Baseline research information may be shared with the MICRA treatment staff for feedback purposes, but will not be shared with SWNARC treatment staff.

#### **4.1.1 On-Site Communication of Information**

Maintaining the boundaries between the data collection and the treatment arms is not always an easy task. The importance of the separation between the phases is embodied in the fact that different staff performs these two vital functions. Staff collecting data should be trained in maintaining this distinction. Staff should also acquire skills and resources to deal with situations that challenge the boundaries between treatment and data collection phase.

Outlining the flow of communication (what can be communicated and to whom?) is another way to maintain boundaries between research and treatment staff. The Communication Table in Appendix F outlines information that can be communicated between research and treatment staff.

**Table 4.1 Baseline Assessments**

	Time
BAC (only if baseline is on a different day than the screen)	3
Intercept Oral Fluid Drug Screen	5
RA-Administered Interview Measures	
Form 90 Interview	40
Addiction Severity Index	60
Locator Form	10
Self-Report Questionnaires	
Risk Behavior Questionnaire	10
Inventory of Drug Use Consequences-2R	15
Brief Symptom Inventory 18	5
Beck Hopelessness Scale	5
Condom Use Self-Efficacy	15
Alcohol/Drug Use: Confidence & Temptation	10
Scale of Ethnic Experience	15
Microaggressions Scale	15
Daily Spiritual Experience Scale	8
Total Time (minutes)	226
Total Time (hours)	3.77

**4.2 Biological Assessments**

**4.2.1 Breath Alcohol Content**

If the participant completes his or her screening on the same day as the baseline assessment, then the BAC does not have to be repeated. This should be noted on the Baseline Checklist. If the baseline assessment is on a separate day, then the participant must be given a BAC before completing the assessment. The results of the BAC are recorded on the baseline checklist. If the BAC is less than or equal to .05, continue on to the oral fluid screen. If the BAC is > .05, the RA will inform the individual of his or her BAC level and that it is not safe to drive. The RA will inquire about the individual's transportation to and from the screening. The RA may call someone to pick up the participant, or let him or her stay in the office until his or her BAC is less than or equal to .02. If the person insists on driving away, the RA will inform them that they have to call the police but will not try to restrain him or her from leaving the building. If BAC > .05, the individual must reschedule the baseline assessment for another day. Even if an

individual has a BAC of .05 or lower, the RA has the right to not continue with the assessment if the individual smells like alcohol or seems intoxicated or impaired by other drugs. It is important to be safe. In such cases, the RA will ask the person to reschedule for another day.

#### **4.2.2 Oral Fluid Drug Screen**

The Intercept Oral Fluid Drug Screening will be given at each research interview. The screening tests for the following drug categories: Amphetamines, Methamphetamines, Benzodiazepines, Cannabinoids, Cocaine, Opiates, and Oxycodone. The participant will rub a foam swab against their cheek for three minutes and then insert the swab into a fluid-filled vial. Only the participant's identification number will be written on the vial, and the vial will then be sent to a lab in Virginia via Fed Ex. The sample should be sent to the lab within a week of collection to obtain the best results. The PI and RA are able to access results through the Alere Website (<https://www.scitest.us/>; On-line Reporting Tab).

### **4.3 RA-Administered Assessments (\* = used in Personal Feedback Report for MICRA)**

#### **4.3.1 Form 90 Interview\***

The Form-90 obtains primary outcome data through a detailed, comprehensive assessment of daily alcohol and drug use patterns in the past 90 days. The measure uses a modified calendar review method to assess daily alcohol and drug use patterns and BAC/number of standard drinks on the heaviest day of drinking.

#### **4.3.2 Addiction Severity Index - Southwest Native American Adaptation\***

A second key domain in outcome assessment is the measurement of adverse consequences of use. Our standard instrument here will be the Addiction Severity Index (ASI) Southwest Native American Adaptation, a structured interview that has been in routine use at CASAA for over a decade and that was adapted for use in this Southwest Native American tribe. The ASI evaluates severity of life problems in a variety of areas, and it has well-established psychometric characteristics (McLellan, 1985).

#### **4.3.3 Locator Form**

The Locator Form is a standard CASAA assessment instrument. It provides information about contacts that know the participant and would be able to locate them if the RA is unable to contact the participant directly. The Locator Form is filled out in full at the baseline assessment and updated at each follow-up assessment, or whenever the RA has contact with the participant. Information from the locator form will be used to call, visit, or text message the participant, or call the participant's contacts in order to reach the participant for the follow-up interviews.

### **4.4 Self-Report Questionnaires (\* = used in Personal Feedback Report)**

#### **4.4.1 Inventory of Drug Use Consequences – 2R (Recent)\***

The Inventory of Drug Use Consequences (InDUC-2R) measures consequences in the previous four months from drinking alcohol or using drugs in five domains: physical, interpersonal, intrapersonal, impulse control, and social responsibility.

#### **4.4.2 Self-Efficacy and Situation Temptation Scales (ADUSES Part I and II)\***

The Self-Efficacy and Situation Temptation Scales (DiClemente, Carbonari, Montgomery, & Hughes, 1994) are two 20-item questionnaires with similar items. The Situation Temptation scale measures how tempted an individual would be to use alcohol or drugs in a particular situation; the Self-Efficacy scale measures how confident an individual is to abstain from using alcohol or drugs in those same situations.

#### **4.4.3 Brief Symptom Inventory 18\***

The BSI 18 is a brief self-report questionnaire whose 18 items yield continuous scores for the 3 dimensions of anxiety, depression, and somatization, as well as an overall global severity index. Derived from the SCL-90, it provides a symptom picture for the past week.

#### **4.4.4 Beck Hopelessness Scale**

Since suicide and hopelessness are comorbid with substance abuse and a concern for many Native American populations, we will use the Beck Hopelessness Scale (BHS) to assess these domains. The BHS consists of 20 items, is quick to administer and is less intrusive than a clinical interview.

#### **4.4.5 Risk Behavior Questionnaire\***

The Risk Behavior Questionnaire (RBQ) is a shortened version of the Risk Assessment Battery (Navaline et al., 1994) with added questions from the Sexual Behavior Interview (SBI; Calsyn et al., 2009). It will provide a behavioral measure of sexual practices in the past 4 months. It includes questions on the frequency of unprotected sex by partner type, the number of partners in the assessment period, and percentage of time sex occurred under the influence of substances.

#### **4.4.6 Condom Use Self-Efficacy**

The Condom Use Self-Efficacy Scale (CUSES; Brafford & Beck, 1991) will be given to measure confidence to use a condom, persuade a partner to use a condom, and use a condom while under the influence of substances. This measure has demonstrated excellent reliability across samples ( $\alpha = .83-.93$ ).

#### **4.4.7 Scale of Ethnic Experience**

In order to characterize the sample, it is important to ask about cultural identity and discrimination. The Scale of Ethnic Experience (SEE; Malcarne, Chavira, Fernandez, & Liu, 2006) consists of 32 items and yields four subscales of cultural identity, mainstream comfort, social affiliation and perceived discrimination for one's ethnic group.

#### **4.4.8 Microaggressions Scale**

The Microaggressions Scale (MA; Walters, 2010) measures daily events that communicate negative or hostile messages towards American Indians and that collectively can negatively impact mental health.

#### **4.4.9 Daily Spiritual Experience Scale**

The Daily Spiritual Experience Scale (Underwood & Teresi, 2002) taps feelings of connectedness to spirituality and has been adapted for the Southwest Native American people.

#### **4.5 Ending the Baseline Assessment**

When all assessment instruments have been completed, the RA will provide the participant with a \$50 gift certificate to Halona Plaza (see Incentives SOP for details). The RA will enter the completed baseline assessment date into the Participant Enrollment log, record the estimated 4-month follow-up date, and provide the participant with an appointment card for the 4-month follow-up. Follow-up appointments should be scheduled approximately 2 weeks before the estimated 4-month follow-up date.

In Phase II, the RA will open the randomization envelope (see Chapter 5 for details) and inform the participant of their treatment assignment. For those assigned to SWNARC, the RA will inform the participant that his or her referral packet will be sent to SWNARC, and that SWNARC will call to schedule a date and time for the participant to go to SWNARC and complete the intake process. For Phase II participants assigned to MICRA and all Phase I participants, the RA will walk them over to a counselor's office and have them schedule the first treatment session. If all counselors are occupied, the RA will schedule an appointment for the participant with a counselor.

## **Chapter 5: Randomization (Phase II Only)**

### **5.1 Introduction to Randomization**

Randomization only applies to Phase II participants; all Phase I participants will receive MICRA. Randomization divides the study participants equally between two groups using a chance process that guards against the possibility that a certain type of participant (e.g., those with more severe substance use) ends up in one study condition more often than in another. Participants will be randomized upon completion of the baseline interview. Eighty individuals will be randomized (40 per treatment condition). No provisions have been made for replacement of participants that do not adhere to the protocol once treatment intervention has been assigned, although research interviews with these participants will continue to determine how they are doing at the follow-up interviews.

### **5.2 The Randomization Process**

Once participants have completed all baseline assessments, the RA will determine the treatment assignment by pulling out the envelope with the appropriate number. Sixty cards have been numbered with 30 “Ms” and 30 “Zs” (M = MICRA; Z = SWNARC), placed in individual envelopes, and shuffled thoroughly. The envelopes are numbered sequentially from one to 60. The first person that consents and completes the baseline will receive the treatment assignment from envelope 1, the second individual will receive the assignment from envelope 2, and so on. The treatment assignment will be recorded on the Baseline Checklist. The envelopes will be shuffled by the PI, Co-PI, and RA before Phase II begins. A second randomization process will occur to accommodate the increase in recruitment (from 60 to 80) that was approved by the National Institute of Drug Abuse (funding agency) in March of 2012. Ten additional cards will be labeled with “MICRA” and ten will be labeled as “SWNARC.” These cards will be placed in envelopes and shuffled, and the envelopes then will be labeled from 61 to 80. Similar to the process described above, the 61st through 80th participants will receive the treatment assignments listed on the cards in the envelopes corresponding to numbers 61 through 80.

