### **6.3 Follow-up Assessments**

Follow-up assessments are listed in Table 6.1. Phase I participants do not have a 12-month follow-up; because of this they will complete more questionnaires at the 8-month follow-up than the Phase II participants do. The procedures for the BAC and the oral fluid drug test are provided in Section 4.2. Descriptions of the assessments in Table 6.1 are given in Sections 4.3 and 4.4. Several questionnaires inquire about a different time period when given at follow-up than when given at baseline. These questionnaires include (period of interest at follow-up in parentheses):

Form-90 Interview (time since last research interview)

Addiction Severity Index (past 30 days and time since last research interview)

SCID (time since baseline interview)

Inventory of Drug Use Consequences-2R (time since last research interview)

\*\*Locator form from the baseline interview is pulled out and updated at each follow-up and whenever study staff has contact with the participant

All other questionnaires inquire about the same time period at each research interview.

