### *Appendix C: Phase II Sample Screening Script*

(Assessment process can be interpreted in the Southwest Native American Language if participant does not fully understand English)

Good Morning/Good Afternoon. My name is [name], I am the research/administrative assistant with the Southwest Native American MICRA Project. I am the person who collects research data before, during and after treatment in order to evaluate the effectiveness of treatment. I will be the person in charge of doing the screening and consent process, the baseline as well as the 4, 8, and 12 month follow up visits.

Thank you for coming in today. I really appreciate your patience in getting together to meet with one another. It shows how much determination you have to help yourself. I understand you have expressed interest to participate in the Research study and that we have received your referral from the Southwest Native American Recovery Center.

We will be starting out by doing the screening & consent process to determine if you are eligible for the study. It will take at least an hour to do the necessary paperwork to determine your eligibility. Do you have any questions before we proceed?

Let's start out by discussing a little bit about the study. May I share with you what the MI/CRA Study is about? Southwest Native American Pueblo in collaboration with the University of New Mexico has teamed up to do a research study to see if Motivational Interviewing (MI) and Community Reinforcement Approach (CRA) will work for our Southwest Native American People. This is a non-confrontational and strength based model that focuses on building motivation for change. You will receive outpatient substance abuse counseling and with your permission we would like to pay you for your participation in the research study which will be in the form of a gift certificate after the initial intake interview and cash incentives at 4, 8, 12 month follow-ups. We will not force you to stay in the study if you do not wish to continue and we will honor and respect your decision. I would also like to inform you that I will not be in charge of your treatment process as you will be working one on one with a counselor and that all information obtained from you during your follow up assessments will not be shared with your counselor but baseline information may be shared for feedback purposes.

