There are two programs participating in the study, the MICRA project and Southwest Native American Recovery Center. If we find that you are eligible for the study, we will put your name in a randomization program which means you will receive your treatment services either with MICRA or Southwest Native American Recovery Center. The purpose of randomization is to make sure that the groups of participants who receive the two treatments are balanced in terms of things like age, education, etc. I will not know which treatment you will receive, and you must be okay with not knowing which treatment you will get. Do you have questions about the randomization process? If you are assigned to SWNARC we will not lose all contact with you. I will continue to stay in touch with you by doing follow ups and to provide you with your incentives.

Do you think this study might be something you're interested in? (Depending on whether the client is interested...) Wonderful that you would like to take part in the

research study. The next step is to determine if you would be eligible to take part in the study, but first we would need to do an alcohol breathalyzer test before we proceed. Each participant who agrees to continue with the screening is asked to voluntarily provide us with a BAC. Your BAC information will not be shared with your referring source; again your information will be kept confidential. With your permission, I would like to administer the BAC. (If BAC is beyond .05, then participant must be informed that their BAC is higher than expected and reschedule the Screening and Consent Process to another date and time).

Another important item I would like to stress is that all information gathered while participating with the project will be kept confidential and the only time any information can be released is if you give us permission by signing a Release of Information Form.

Next we will be completing a form about your alcohol and drug use. It will take approximately 30 minutes to complete. I will be asking you questions that pertain to alcohol or substance use within your lifetime. (After completing the SCID, the RA will determine whether the participant meets the eligibility criteria for substance abuse or dependence. If participant is eligible, the consent form can be explained more in depth and questions will be answered if the participant has any prior to signing the form. The HIPAA Form will be signed during this time).

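### The research assistant who opens the envelope and announces the arm also conducts the follow-up Form 90 interview, so the interview part of the primary outcome is collected unmasked by procedure

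*Protocol*

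**What the plan says.** **Assignment.** Once baseline is complete, "the RA will determine the treatment assignment by pulling out the envelope with the appropriate number" (Protocol 5.2). Section 4.5 adds that "the RA will open the randomization envelope (see Chapter 5 for details) and inform the participant of their treatment assignment". She then walks MICRA participants to a counselor or books them, and tells SWNARC participants how their referral will proceed. On the arm itself, "The treatment assignment will be recorded on the Baseline Checklist" (5.2). The RA already uses that checklist for breath alcohol results (4.2.1).

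**Follow-up.** In the Phase II script (Appendix C) the RA introduces herself as the person "in charge of doing the screening and consent process, the baseline as well as the 4, 8, and 12 month follow up visits". She says she will also do the follow-ups of participants assigned to SWNARC. The follow-up schedule under 6.3 lists the Form 90 among the RA-administered interviews at all three visits.

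**Outcome.** Section 4.3.1 states: "The Form-90 obtains primary outcome data". Section 7.5 derives percent days abstinent from the Form 90 and the saliva tests and sets the main analysis at 4 months.

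**Separation of roles.** Sections 4.1, 4.1.1 and 6.1 and Appendix F separate research from treatment staff and restrict what they may exchange about a participant. No section shown provides a masked outcome interviewer.

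**The concern.** The Form 90 is a calendar interview. The interviewer helps the participant reconstruct daily alcohol and drug use, at follow-up for the whole time since the last research interview. How hard she probes, and how she resolves a vague answer, can depend on what she expects of the arm. Aim 4 of this pilot is to estimate effect sizes for MICRA. A difference in interviewing between arms would enter that estimate directly, and a larger sample would not remove it.

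Participants and counselors cannot be masked in a counseling trial. The interviewer is a different case: she knows the arm because the protocol gives her a clerical task that others could do.

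**Working it through.** The protocol states no figure on this point, so the check traces duties and counts what they reach.

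**1. Does one person both learn the arm and interview?**
- Pulls the envelope: RA (5.2).
- Opens it, announces the arm, escorts or books MICRA participants: RA (4.5).
- Conducts the 4-, 8- and 12-month visits in both arms: the same RA (Appendix C).
- Administers the Form 90 at those visits: RA (schedule under 6.3).

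The arm is known to her at baseline, about four months before the first outcome interview.

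**2. Does any safeguard mask her?**
- The staff separation and Appendix F limit what counselors and the RA tell each other. They cannot withhold what she has herself announced.
- Phase 1 certifies the RA in assessment administration (1.2), and a monitor reviews form completion monthly (7.1.4). Both standardize her work; neither hides the arm.
- The saliva test is read by a laboratory (4.2.2). The primary measure names alcohol, amphetamine, cannabis, cocaine and inhalants, which is 5 substances. The panel includes amphetamines, cannabinoids and cocaine, which is 3 of the 5; alcohol and inhalants are not on it. It is one sample per visit against a daily record of about four months.
- Breath alcohol is taken at each follow-up, but 7.5 does not name it in the primary measure.

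**3. How many endpoint interviews are affected?**
- Planned at 4 months: 80 of 80.
- At the 80% follow-up target in 6.1: 0.80 × 80 = 64, or 32 per arm if losses are equal.

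**4. What would a given bias do? (illustration under assumption)**
The protocol gives no figure for interviewer bias, so I assume a shift of b standard deviations in percent days abstinent between arms, with no true effect. I use a two-sided 5% test (7.5 sets alpha at .05 without stating sidedness) and a simple two-mean normal approximation, not the planned MANOVA with baseline covariates:

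rejection probability = Φ(b/SE − 1.96) + Φ(−b/SE − 1.96), with SE = √(2/n).

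For n = 40 per arm, SE = 0.2236. At b = 0.2, b/SE = 0.894, giving 0.1433 + 0.0022 = 0.1455. For n = 32, SE = 0.25.

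| Assumed shift b | n = 40 per arm | n = 32 per arm |
|---|---|---|
| 0.1 SD | 7.3% | 6.9% |
| 0.2 SD | 14.6% | 12.6% |
| 0.3 SD | 26.9% | 22.4% |

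These show sensitivity only. Nothing in the protocol says that a shift of any of these sizes would occur.

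**The case against.** The other side has several fair points.

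- **It is a design choice in a developmental pilot, and the protocol never claims a masked assessor.** This stands: nothing is contradicted. It lowers the weight of the point but does not remove it, because the pilot is meant to yield effect sizes and sets an alpha level.
- **The RA is certified and monitored.** True, and it may reduce uneven probing. It does not mask her.
- **Other routes would still reveal the arm.** The RA has access to the folder of session tapes (5.5). Baseline data may go to MICRA staff but not to SWNARC staff (4.1). Section 6.2.2 encourages discussions between research and clinical staff about specific participants. Conversations about dropping out may touch on the assigned treatment (6.2.3 and the risk-factor table). Interviews are generally held in the MICRA offices (6.1). This stands, and a fix that only moved the envelopes would be incomplete.
- **The immediate hand-off has value.** Participants who never start treatment are not replaced (3.1), and loss of contact is a listed risk. This is a real cost.

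Three stronger readings are tempting but not supported:

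- **That the script contradicts the procedure.** In Appendix C the RA says "I will not know which treatment you will receive". She says it at screening, before any envelope is opened, so it is true when spoken and promises nothing about outcome masking.
- **That allocation is compromised.** Section 5.2 states "The envelopes will be shuffled by the PI, Co-PI, and RA before Phase II begins" and does not say who keeps the envelopes. But they are numbered, used in sequence, and opened only after consent and a completed baseline. Section 3.3 also mentions a second RA at CASAA, so that the field RA took part in the shuffling is likely rather than certain. The point here does not depend on it.
- **That every follow-up interview counts equally against the main result.** The main analysis is at 4 months, so the 4-month interviews are the relevant count.

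**Conclusion.** The point holds in a limited form. Following the protocol as written, the person who conducts the Form 90 knows the arm at every planned 4-month interview: 80, or 64 at the follow-up target. The interview component of percent days abstinent is therefore open to an avoidable interviewer bias, with a partial laboratory check on three of five substances. The second key measure, the InDUC, is a self-report questionnaire and less exposed to the interviewer.

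This rests on reading the RA in 4.5, 5.2 and Appendix C as one person, which the script supports. It also takes the Form 90 as the source of the daily record; 7.5 elsewhere refers to a timeline follow-back, but the Form 90 is the instrument scheduled.

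The size and direction of any bias cannot be derived from the document. A reader might infer that the results would be invalid; the protocol gives no basis for that. This is an inexpensive improvement, not a fatal flaw.

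**What to change.** - **Envelopes (4.5, 5.2, 5.3).** Have existing staff who do no outcome interviews, for example the project coordinator with a named backup, prepare, hold and open the envelopes in order of baseline completion. The same staff give the assignment to the participant and the program and make the first booking, the same day where possible. The 30/30 then 10/10 scheme is unchanged.
- **Record.** Keep the arm in a log the RA does not see, instead of on the Baseline Checklist.
- **Other routes.** Remove the RA's access to the session-tape folder (5.5). Have someone else release baseline feedback data (4.1). Keep the arm out of joint staff discussions and of the RA's conversations about dropout (6.2.2, 6.2.3).
- **Follow-up.** Ask participants, in the Appendix C script and at visits, not to reveal their arm. Record at each follow-up whether the RA knows it, and report this with the effect-size estimate.
- **If envelopes are already in use.** Apply this to the unopened ones and to 61–80, and record the RA as unmasked for earlier participants.

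**Cost.** At most 80 contacts by existing staff, one log, and edits to the sections named, the follow-up form and Appendix C. No extra assessor is needed. The downsides are losing the RA's immediate escort to a counselor and relying on coordinator availability that the protocol does not state. Masking will be only partial, because interviews are generally held where MICRA clients attend and participants may disclose. The two-week limit for starting treatment runs from randomization (3.1), so a short wait before the envelope is opened does not use it up.
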